This study is a prospective, randomized (1:1 medical record based MTM, the intervention to non-medical records based MTM, the control or standard of care), clinical trial, comparing disease-specific clinical and humanistic outcomes in 200 adult African-Americans with HIV (1:1 men:women) and either DM and/or HTN. Data will be collected from individual participants for a 2-year period. Potential participants will be identified and recruited as detailed in the recruitment section. A study screen visit will be arranged.

Screening visit (Visit 1)

Protocol version 9 October 2023

Medical record vs. Non-medical record community pharmacy based MTM study

Page 7 of 31

The screen visit is when the participant will be consented. The screen visit may take place over the phone or in-person. Either the PI or SC will conduct the screening visit. For screening procedures done over the phone, the necessary documents will be sent to the participant's email through Docusign in an encrypted link. The PI or SC will schedule a meeting through zoom to consent the participant and guide them on the pages that requires their signatures. For participants who do not have access to internet the consent form will be mailed out to them. Later the PI or SC will schedule a meeting over the phone to obtain the consenting process and guide the participant on the pages that required their signature. A **SCREENING CHECKLIST** has been developed and is attached to facilitate the NTRIRB review of the steps being taken by the research team when conducting the screening visit (Visit 1). This (and all) checklists are for use only by research team personnel. Participants will not have to complete the survey at screening visit. Participants are not compensated for completing the screening visit.

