2) **Data Analysis and Data Monitoring** – Describe plans for statistical analysis of data when appropriate. If a data safety monitoring committee is appropriate to protect the safety and/or welfare of subjects, describe its operation (e.g., membership, stopping rules and frequency of review).

The diseases being used to validate HIV-CMTM effectiveness are HIV, DM and HTN. For HIV, disease control is defined as plasma HIV-RNA of < 20 copies/mL. Standard of care recommends follow-up based on viral load. (19) For DM, self-monitoring of blood glucose is less reliable than quarterly A1c levels (goal of \leq 7%) which is monitored every 3 months. In HTN, goals vary based on comorbid conditions as follow-up varies with medications. As AA have 2-3 higher incidental rates of stroke compared to whites. (Howard). As a 10 mmHg difference in systolic blood pressure is shown to reduce stroke rate by 24% in AA, a decrease in systolic blood pressure reductions of 10 mmHG [or attainment of blood pressure goal] was selected as the primary measure for effectiveness on HTN. Medical record blood pressure will be the primary source for analyses as ultimately, it is the information collected by the diagnostician that is used for decisions.

Two sample t-test for continuous outcomes (viral loads) and chi-square for categorical outcomes (blood pressure under control or not) would be used to assess significance at the 0.05 level.

DATA AND SAFETY MONITORING PLAN

There are no medical procedures or prescription changes that can occur as part of this study that are not first authorized by the patient's medical provider. A data safety monitoring plan has been presented and approved by the NIMHD Program and Science Officer that reflects the low safety risk to participants, from a medical perspective. The **DATA SAFETY PLAN** is attached. The risks to participants due to protection of information and how information is safely maintained is addressed elsewhere in the protocol.

3) **Data Storage and Confidentiality**

Data Security, Collection, Entry, Management, and Quality Control: Only authorized study personnel will have access to the data. All HIPAA research safeguards and protocols for protected health information will be observed. All randomized participants will be assigned a unique identification (UID) number for use throughout the project. This number will be

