Two hundred adult AA with HIV and either/both DM or HTN will be recruited using NTRIRB approved recruitment materials. Once consented, patient gender and comorbidity stratified randomization (i.e., separate randomization by men/women and by DM/HTN) will be used to randomize them into the intervention group or control. Randomization assignment will be controlled by the biostatistician. This will create eight groups: men with DM receiving intervention (1.a.), men with DM receiving control (2.a.), women with DM receiving intervention (1.b.), etc. (Figure 4). Patients with dual diagnosis of DM and HTN will be randomized into either the intervention or control group. Their data will be used in both DM and HTN analyses (after conducting a sensitivity analysis to determine that the dual diagnosis does not confound or bias the results). A random number generator (range 1 to 10,000) will be used for group assignment. UNTHSC biostatistician will be the only unblinded member of the research team to which number corresponds to the intervention or control groups when presenting data during investigator team safety reviews and data safety monitoring plan described.

The primary endpoint for this study will be the health indicators collected at the final follow-up visit comparing the corresponding intervention and control groups (e.g., intervention vs. control for men with diabetes). We computed the power and sample size based on the effect sizes estimated from our previous CDC-funded demonstration project where observations from 201 African American HIV patients at baseline whose viral loads were either detectable (>20 copies/mL) or their CD4 counts were <200 cells/mcL at baseline. Of these, 171 (85%) showed improvement (viral loads became undetectable or CD4 counts became >200 cell/mcL) at follow-up after receiving quarterly HIV-CMTM. Based on these results and even assuming a very conservative effect of 45% improvement for the control group receiving standard of care projects that a comparison between intervention and control will require 22 subjects per group. This enrollment volume enables attaining a power of at least 80% at the 0.05 level of significance for each of the comparisons. As some attrition is expected, we will recruit 25 patients per group for a total of 200 patients. We also note that the sample sizes are very likely larger as the subjects with a dual diagnosis of diabetes and hypertension will be included in the analyses, but are not included in the

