sample size computations shown above. We also conducted additional power analyses based on this sample size to verify that the analyses will be sufficiently powered when the outcome measures are treated as continuous (testing means) rather than dichotomous.

Control Group Medical Record Viewing by Study Pharmacist

Pharmacists are not prohibited from requesting the complete medical record from a medical provider pursuant to normal counseling and care provided, this is just rarely (if ever) done. Pharmacists routinely contact medical providers to recommend changes to medications. If the study pharmacist, in the course of providing MTM to participants in the control group, contacts a medical provider, this will not change the status of the control group participants. If, however, the study pharmacist feels compelled to obtain the entire medical record for a participant in the control group, s/he will notify the participant and PI/SC. Should the study pharmacist inadvertently gain access to a control participant's medical records (participant brings medical records themselves to the MTM session and the study pharmacist uses the complete medical record for the purposes of MTM), the participant will not be discontinued. In either case, the participant will not be discontinued. The time point at which the study pharmacist gained access to the medical record for participants in the control group will be noted and this will become a controlled variable in the analyses.

2) Describe both *Inclusion AND Exclusion Criteria*.

Inclusion criteria:

- >/= 18 years old or older at time of screening
- Male or female
- Self identifies as African-American or black
- Able to read and speak English sufficiently well enough to be interviewed by study pharmacist (as determined at screening visit by PI/SC)
- Confirmed diagnosis of HIV (medical record)
- Confirmed diagnosis of diabetes, hypertension, or both (medical record)
- Stated agreement to comply with study requirements during screening visit
- Able and willing to provide written informed consent
- Willing to notify study pharmacist if becomes pregnant during study
- Expresses a willingness to participate in all study-related assessments and adhere to study requirements
- Willing to notify research team if planning to relocate
- Willing to notify research team if incarcerated at any point during study

Exclusion criteria: (whether discovered at time of consent or after review of medical records)

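### Dual-diagnosis participants have no stated diagnosis stratum and no clear place in the 200, and the planned tests do not adjust for dual status

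*Combined protocol and SAP*

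**What the plan says.** **Eligibility and the 200.** The inclusion criteria (section F.2) require "Confirmed diagnosis of diabetes, hypertension, or both (medical record"), so three diagnosis groups are eligible: DM only, HTN only, and both. The design paragraph of section E.1 describes "200 adult African-Americans with HIV (1:1 men:women) and either DM and/or HTN". Section F.1 agrees: "Two hundred adult AA with HIV and either/both DM or HTN will be recruited".

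**Randomisation.** Section F.1 stratifies by sex and comorbidity, explained as "separate randomization by men/women and by DM/HTN", and continues: "This will create eight groups: men with DM receiving intervention (1.a.), men with DM receiving control (2.a") and so on. Of the third diagnosis group it says: "Patients with dual diagnosis of DM and HTN will be randomized into either the intervention or control group". It then states that their data serve both disease analyses, after a sensitivity analysis intended to show that dual diagnosis does not distort the results. Assignment is by a random number generator. No blocks are described.

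**Sample size.** Section F.1 derives 22 per group, recruits 25 per group to allow for attrition, and totals 200. It says dual-diagnosis participants are left out of this computation, and that the sample sizes are therefore probably larger than shown.

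**Analysis.** The primary comparison in F.1 is intervention against control within sex and disease, with men with diabetes as the example. Section E.2 names a two-sample t-test and a chi-square test, with no covariate or stratification factor. It also says: "In HTN, goals vary based on comorbid conditions".

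**The concern.** Each disease comparison mixes single- and dual-diagnosis participants, but the stratification is defined only on DM versus HTN. As written, the protocol does not show that the dual share is balanced between arms within, for example, the comparison of men with diabetes. If dual status is related to the outcome, a chance imbalance shifts that comparison, and an unadjusted test does nothing to correct it. The cells are small, so such imbalances are not rare.

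The second problem is the count. Eight single-diagnosis groups of 25 use every one of the 200 places, while E.1 and F.1 place dual participants inside the 200. A reader cannot tell what 25 per group refers to, nor whether the expected gain in cell size applies to both diseases.

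**Working it through.** **1. The plan's own figures.** Inputs from F.1: response 0.85 (171/201 = 0.851) against 0.45, alpha 0.05 (taken as two-sided), power 0.80. With the pooled-variance formula and mean proportion 0.65:

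n = [1.960 x √(2 x 0.65 x 0.35) + 0.842 x √(0.85 x 0.15 + 0.45 x 0.55)]² / 0.40² = (1.322 + 0.515)² / 0.16 = 21.1, rounded up to **22**. Power at 22 is 0.817.

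22/25 implies 12% attrition, and 8 x 25 = **200**. Both figures reproduce.

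**2. Strata.** Sex (2) x diagnosis (2) x arm (2) = 8, the stated number of groups. The eligible population has three diagnosis levels: 2 x 3 x 2 = 12 combinations. Figure 4 is not available, but a count of eight leaves no room for a separate dual stratum.

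**3. Chance imbalance.** Assume D dual participants of one sex, assigned by independent 1:1 draws. The chance that one arm receives at least two thirds of them is 2 x P(X ≥ ⌈2D/3⌉), X ~ Binomial(D, 0.5):

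| D (assumed) | Split at least as uneven as | Probability |
|---|---|---|
| 10 | 7:3 | 0.34 |
| 14 | 10:4 | 0.18 |
| 15 | 10:5 | 0.30 |
| 16 | 11:5 | 0.21 |
| 20 | 14:6 | 0.12 |

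The values are not smooth in D because the counts are discrete, so the range matters more than any single entry.

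**4. What an imbalance could do.** Assume 25 single-diagnosis participants per arm, 15 dual participants split 10:5, and response rates 20 points apart by dual status. The dual shares are 10/35 = 28.6% and 5/30 = 16.7%. The shift is (28.6% − 16.7%) x 20 points ≈ 2.4 points, against the planned difference of 85 − 45 = 40 points.

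**5. Cell sizes if the 200 includes dual participants.** With D now the total number of dual participants, 200 − D people each count in one disease analysis and D count in both. The eight analysis cells therefore average (200 + D)/8, which is never below 25.

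The four DM cells average (number with DM)/4. They reach 25 only if 100 of the 200 (50%) have DM, alone or with HTN. Assumed example: 10% DM only, 60% HTN only, 30% dual. DM cells average 200 x 0.40/4 = 20 and HTN cells 200 x 0.90/4 = 45. After 12% attrition, power in the DM cells is 0.72.

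**6. If dual participants were dropped.** Assume a dual share d and an even split of single diagnoses. Cells hold 200(1 − d)/8: 22.5, 20 and 17.5 for d = 10%, 20% and 30%. After 12% attrition, power is 0.77, 0.72 and 0.66.

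**The case against.** The protocol does not overlook these participants. It says they are randomised, analysed in both disease sets, checked in a sensitivity analysis and left out of the sample size. On a natural reading they are at least stratified by sex, since the stratified scheme applies to all 200. Section F.1 is silent on their diagnosis list; it does not say there was none. All of this stands. What remains open is which list was used, where they sit in the 200, and what the sensitivity analysis is. It has no method, criterion or consequence, and step 6 shows that the consequence matters.

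A reader might infer that dual status is known to affect both outcomes. The documents do not support that. E.2 says HTN goals vary with comorbid conditions, without naming DM, and offers a 10 mmHg systolic reduction as an alternative to goal attainment. For DM it gives a single HbA1c target with no dependence on comorbidity. An influence on HTN goal attainment is plausible; an influence on DM control is not documented. Chance imbalance under 1:1 randomisation is also not systematic bias, and step 4 suggests a modest shift relative to the planned effect.

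A reader might also infer a general loss of power, or a need for twelve groups of 25 (300 participants). Neither follows. Pooling dual participants enlarges the cells on average, and a larger total would be needed only if dual participants were to form a separately powered comparison, which the plan does not propose.

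**Conclusion.** The point holds as a gap in stratification and analysis together with an inconsistency in the count. Three diagnosis groups are eligible and two diagnosis levels are stratified. No diagnosis stratum is named for the third group, and the planned tests do not adjust for it. With 10 to 20 dual participants of one sex, the chance of a 2:1 or worse split lies between 12% and 34%. This assumes independent draws and an unknown number of dual participants.

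The 200 cannot both be filled by eight single-diagnosis groups of 25 and include dual participants. It is not a sample size error, since 22 and 200 reproduce. The expectation of larger cells is right on average over the eight cells but is not assured for each disease: DM cells fall below 25 on average if fewer than half of the 200 have DM.

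The point deserves correction because the remedy costs almost nothing, not because a large bias has been shown.

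**What to change.** - **Primary analysis.** Keep the within-sex comparisons of section F.1 and adjust each for single versus dual diagnosis, in place of the unadjusted tests in E.2. For binary outcomes, use for example a Cochran-Mantel-Haenszel test over single/dual within each sex-by-disease comparison. For continuous outcomes, add a single/dual term to the model. Do not pool across sex in doing so, as that would change the primary comparison.
- **Sensitivity analysis.** Define it as the same comparison without dual participants, and state how a differing result will be read.
- **Randomisation text.** State how dual participants were actually assigned. Do not rewrite F.1 as twelve randomised groups: section F.5 reports recruitment complete as of 31 October 2022, so that could describe an allocation that never took place.
- **Counts.** State whether the 200 includes dual participants. Replace the expectation of larger samples with actual numbers by sex x (DM only, HTN only, both) x arm.

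Diagnosis is confirmed from medical records before group assignment (E.1), so no new data are needed. The cost is slightly more analysis work and some sparse strata.

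### The primary comparison is illustrated and sized within four sex-by-disease cells at 0.05 each, with no sex-combined test per disease and no multiplicity rule specified

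*Combined protocol and SAP*

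**What the plan says.** Section A (Specific Aims) asks about change in control of diabetes and/or hypertension in African-American adults with HIV. It states no sex-specific hypothesis.

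Section F.1 (Sample Size) stratifies randomisation by sex and by disease: "This will create eight groups: men with DM receiving intervention (1.a.), men with DM receiving control (2.a.), women with DM receiving intervention (1.b.), etc". It describes the primary endpoint as health indicators at the final follow-up visit, "comparing the corresponding intervention and control groups (e.g., intervention vs. control for men with diabetes". On sizing, it "projects that a comparison between intervention and control will require 22 subjects per group" and adds: "This enrollment volume enables attaining a power of at least 80% at the 0.05 level of significance for each of the comparisons". Allowing for attrition, "we will recruit 25 patients per group for a total of 200 patients". The 85% input comes from the pilot project, where, of 201 patients, "171 (85%) showed improvement (viral loads became undetectable or CD4 counts became" higher than 200. The 45% control rate is the plan's assumption.

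Other wording points to the level of the disease or the arm. Section E.1 describes a 1:1 trial "comparing disease-specific clinical and humanistic outcomes in 200 adult African-Americans with HIV". It also says that records are needed from both arms so that the arms can be compared. Section F.1 says of participants with both diagnoses: "Their data will be used in both DM and HTN analyses". Section E.2 (Data Analysis and Data Monitoring) names a two-sample t-test and a chi-square test at 0.05 but does not say which groups they compare.

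The public text gives no multiplicity adjustment, no hierarchy and no rule for combining cell results. Figure 4 and the attached data safety plan are not available in it.

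**The concern.** The aim asks one question per disease, while the stated comparison and the sample size are built on four cells: men with DM, women with DM, men with HTN and women with HTN. The plan does not say whether the primary test is run in each cell or across the sexes within a disease, or what set of results would support Aim A.

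Two things are at stake. If the four cells are each tested at 0.05 and any one may be cited for Aim A, the overall false-positive rate is well above 5%. And a cell-level test uses half the participants available for a question that is not about sex, which costs power, most of all if the true effect is smaller than the one assumed.

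**Working it through.** **Inputs.** From F.1: rates 0.85 and 0.45, 22 required and 25 recruited per group, eight groups, power at least 80%, level 0.05. From E.1: 1:1 allocation. Sidedness is not stated, so two-sided tests are assumed. The alternative of 65% vs 45% is also an assumption, used only to show a smaller effect.

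**1. Reproduce the plan's figure.** Pooled-variance formula without continuity correction:

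n = [z(α/2)·√(2p̄(1−p̄)) + z(power)·√(p1(1−p1) + p2(1−p2))]² / (p1−p2)², with p̄ = 0.65.

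- √(2 × 0.65 × 0.35) = 0.6745; √(0.1275 + 0.2475) = 0.6124
- n = (1.960 × 0.6745 + 0.8416 × 0.6124)² / 0.16 = (1.3221 + 0.5154)² / 0.16 = 21.1, rounded up to 22
- 22 / 0.88 = 25, so 12% attrition is implied; 8 × 25 = 200

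The stated figure reproduces, and the total follows only if sizing is done cell by cell.

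**2. False positives with four tests at 0.05, any one counting.**

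- Independent tests: 1 − 0.95⁴ = 0.185
- Any dependence (Bonferroni bound): 4 × 0.05 = 0.20

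Participants with both diagnoses enter the DM and the HTN analyses, so the tests are not fully independent. The bound covers this.

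**3. Power per cell against sexes combined.** Power = Φ([|p1−p2|·√n − z(α/2)·√(2p̄(1−p̄))] / √(p1(1−p1) + p2(1−p2))). Combining the sexes gives 2 × 22 = 44 per arm per disease.

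| Rates | Cell, 22 per arm, 0.05 | Cell, 25 per arm, 0.05 | Combined, 44 per arm, 0.05 | Combined, 44 per arm, 0.025 |
|---|---|---|---|---|
| 85% vs 45% | 81.7% | 86.6% | 98.5% | 96.9% |
| 65% vs 45% (assumed) | 26% | 29% | 47% | 36% |

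Example, 22 per arm at 85% vs 45%: (0.4 × 4.690 − 1.3221) / 0.6124 = 0.905, and Φ(0.905) = 0.817.

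A simulated sex-stratified Mantel-Haenszel test with 22 per arm in each sex agrees: 98.6% (0.05) and 96.9% (0.025) at 85% vs 45%; 45% and 36% at 65% vs 45%.

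**4. Keeping four cells with correction.** At 0.05/4 = 0.0125, power at 85% vs 45% is 62% with 22 per arm and 70% with 25. Reaching 80% needs 31 per arm.

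**5. Two diseases.** Two independent tests at 0.05 give 1 − 0.95² = 9.75%. At 0.025 each, the familywise rate is at most 5%.

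**6. Arm-by-sex interaction.** Assume 85% vs 45% in one sex and 65% vs 45% in the other, 22 per arm per cell, on the risk-difference scale:

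- Standard error: √[(0.1275 + 0.2475 + 0.2275 + 0.2475)/22] = 0.197
- Difference in effects: 0.40 − 0.20 = 0.20, so z = 0.20/0.197 = 1.02
- Power: Φ(1.02 − 1.96), about 17%

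**The case against.** The cell-level definition rests on an example introduced by e.g., and the disease-level wording in E.1 and F.1 could mean that a test across the sexes was intended. Sex is also a deliberate design feature, with equal numbers of men and women and stratified randomisation, and powering each sex separately is a legitimate choice. Whether results reported separately for men and women need familywise control is debated. Dual-diagnosis participants would enlarge the cells by an unstated amount. F.1 mentions further power analyses without results, and the attached data safety plan might hold more detail.

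Much of this stands. It makes the defect one of specification: the level of the primary test and the control of alpha are left open. It does not remove the defect, because the eight groups, the power claim for each comparison and the total of 200 all put the sizing at cell level, and nothing available specifies another test. If separate claims for men and women are intended, the plan should say so, since Aim A does not.

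A reader might infer that the trial will be declared positive on any significant cell, or only if all four are significant. The documents adopt neither rule. The 18.5% is therefore conditional on the first, and the trial should not be charged with the loss of power under the second. Nor should one significant and one non-significant sex cell be read as conflicting: a difference in significance is not evidence of a difference in effect.

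**Conclusion.** The point holds as a gap in specification that should be fixed. The plan illustrates and sizes its primary comparison in four sex-by-disease cells at 0.05 each, for an aim that is not sex-specific, and states neither a sex-combined test nor a multiplicity rule. The arithmetic behind 22 per group is correct.

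The false-positive figure of 18.5%, at most 20%, applies only if any one cell may count as evidence for Aim A. The power figures assume two-sided tests, the planned numbers and the same effect in both sexes. The 85% vs 45% contrast is an HIV viral-load or CD4 effect, so the 97% to 98% for a combined test does not show that the trial is well powered for DM or HTN. At the assumed 65% vs 45%, the combined test still has only 47% power, or 36% at 0.025. The finding of absence is limited to the public text; if Figure 4 or the data safety plan contains a rule, E.2 and F.1 should cite it.

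**What to change.** Amend E.2 and F.1 to make one intervention-versus-control test per disease primary, in all participants with that disease:

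- Stratify by or adjust for sex: Mantel-Haenszel or logistic regression if the outcome is binary, linear regression if continuous.
- Use Holm, or 0.025 each, across DM and HTN.
- Handle study-pharmacist access to control participants' records as F.1 already commits, as a controlled variable.
- Report the four sex-specific cells as secondary estimates with confidence intervals. State that any arm-by-sex interaction test has low power.

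The cost is revised analysis wording and one model per disease. Section F.5 says enrolment is complete, and no design change is needed. The downsides are that sex-specific results become secondary, alpha is shared across two tests, and the primary analysis is settled after enrolment. The change should therefore be dated and should state which by-group data had already been seen, including data presented under coded group numbers at the safety reviews described in F.1.
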